5.2 Secondary Efficacy Variables

All the analyses of secondary efficacy variables will be performed based on the observed cases in the FAS population. No missing data imputation will be considered.

• Percentage of patients who experienced epithelial healing at 4 weeks

The patients who experienced epithelial healing at Visit 4/Week 4 will be determined for study eye similarly as the primary efficacy variable. It will be summarized as a binary goal attainment variable (Yes/No).

• Percentage of patients who achieved epithelial healing at Week 8 and remained healed throughout the follow-up period

The patients who achieved epithelial healing at Week 8 and remained healed throughout the follow-up period will be determined for study eye at Visit 7/Week 32 similarly as the primary efficacy variable. It will be summarized as a binary goal attainment variable (Yes/No) based on the subset of patients who achieved epithelial healing at Week 8, as well as based on the FTS.

• Percentage of patients who experienced complete healing at Week 4 and 8

The patients who experienced complete healing at Week 4 and 8 will be determined for study eye by the investigator and recorded on eCRF. The complete healing is defined as Grade \leq 1 in the central qualifying zone of study eye via FCS (per NEI scale) and no persistent staining in the non-qualifying zones (excluding the superior zone) defined as the absence (Grade 0) of pathological staining via corneal photography. It will be summarized as a binary goal attainment variable (Yes/No).

• Percentage of patients who achieved complete healing at Week 8 and remained completely healed throughout the follow-up period

The patients who achieved complete healing at Week 8 and remained healed throughout the follow-up period will be determined for study eye at Visit 7/Week 32 by the investigator and recorded on eCRF. It will be summarized as a binary goal attainment variable (Yes/No) based on the subset of patients who achieved complete healing at Week 8, as well as based on the FTS.

• Mean change in corneal sensitivity from baseline at 4, 8, and 32 weeks

The corneal sensitivity (cm) in the NEI zone of the study eye as measured by the Cochet-Bonnet aesthesiometer will be summarized as a continuous variable.

• Percentage of patients that achieve an improvement in corneal sensitivity at 4, 8, and 32 weeks

The improvement in corneal sensitivity, defined as change from baseline > 0 (cm) of the study eye, will be summarized as a binary goal attainment variable (Yes/No).

• Schirmer I change from baseline to weeks 4, 8, and week 32

The Schirmer tear test result (mm) in the study eye will be summarized as a continuous variable.

• TFBUT change from baseline to weeks 4, 8, and week 32

The average TFBUT result (sec) of two repeat measurements in the study eye will be summarized as a continuous variable.

• Mean change in BCDVA from baseline to Week 4, 8, and week 32

The logMAR visual acuity score in the study eye will be summarized as a continuous variable.

Percentage of patients that achieve a 15-letter gain in BCDVA at 4 and 8 weeks.

The patients that achieve a 15-letter gain in BCDVA at 4 and 8 weeks will be determined based on Week 4 or 8 logMAR – Baseline logMAR \leq -0.3. It will be analyzed using a binary goal attainment variable (Yes/No).

• IDEEL change from baseline at week 4, 8, and week 32

Subscores will be derived for the following modules, and will be calculated only if at least 50% of the items of the dimension are completed; otherwise, the scores are missing.

Module 1:

Dry eye impact on daily life (27 questions) comprising 3 QoL domains: 1.a "Daily activities limitations", 1.b "Emotional well being" and 1.c "Work limitations". 26 questions will be considered as part of one of these 3 domains. Question 22 will not be considered part of a domain.

1.a: Daily Activities

| Daily activities section | Used in calculation of domain score? |
|---|---|
| 1. Doing close work in the morning or afternoon (such as crossword puzzles, reading, looking at a computer, and/or sewing) | Yes |
| 2. Doing close work in the evening or at night | Yes |
| 3. Driving | Yes |

Statistical Analysis Plan

| 4. Being around and/or using scented products (such as cologne or hairspray) | Yes |
|--|-----|
| | Yes |
| 5. Working on a computer | |
| 6. Going somewhere where there is tobacco smoke or being | Yes |
| around someone who smokes | |
| 7. Wearing contact lenses | No |
| 8. Wearing make-up near or on my eyes | No |
| 9. Flying on an airplane | No |

| Response for questions 1 to 9 | Original | Item score |
|--|---------------|------------|
| | response code | |
| I did not do this activity for reasons other than | 1 | 5 |
| my dry eyes | | |
| None of the time | 2 | 5 |
| A little of the time | 3 | 4 |
| Some of the time | 4 | 3 |
| Most of the time | 5 | 2 |
| All of the time | 6 | 1 |
| I can no longer do this activity due to my | 7 | 0 |
| dry eyes | | |

The response option "I did not do this activity for reasons other than my dry eyes" has a response coded 1 but a scored item value of 5. The original response code is the value to be used for data-entry. The item score is used during the computation of the Daily Activity Limitations Scale Score. Higher item scores are intended to reflect better quality of life (i.e. less limitations on daily activities). Only the first 6 questions are included in the Daily activity Limitations scale score. Questions 7, 8 and 9 are excluded. If 50% (3) or fewer of the 6 questions used in calculating Daily Activity Limitations score have missing item score, then the scale score is calculated by multiplying the mean of the non missing item score by 20. If 4 or more of the 6 item scores are missing then the scale score is not calculated and should be set at missing. Multiplying by 20 transforms the scale score to a 0 to 100 scale, with 0 reflecting the greatest degree of limitations on daily activities measurable by the scale and 100 reflecting the greatest freedom from limitations on daily activities.

1.b Feelings

| Feelings | Used in calculation of domain score? |
|------------------|--|
| 10. Irritability | Yes |
| | |

| Feelings | Used in calculation of domain score? |
|---|--|
| 11. Impatience | Yes |
| 12. Feeling sad | Yes |
| 13. Worry that my dry eyes will get worse | Yes |
| 14. Feeling annoyed | Yes |
| 15. Feeling like my eyes do not look nice | Yes |
| 16. Feeling like I have to make adjustments to my life | Yes |
| 17. Feeling different from other people because of my dry eyes | Yes |
| 18. Feeling like I am always aware of my eyes | Yes |
| 19. Feeling older than I really am | Yes |
| 20. Feeling like people look at me and think I am fine when I'm not | Yes |
| 21. Feeling like there is nothing I can do for my dry eyes | No |

| Response for questions 10 to 21 | Original response code | Item score |
|---------------------------------|------------------------------|------------|
| None of the time | 1 | 4 |
| A little of the time | 2 | 3 |
| Some of the time | 3 | 2 |
| Most of the time | 4 | 1 |
| All of the time | 5 | 0 |

11 questions are included in the Emotional Well-Being score. Question 21 (IDLEMO12) is excluded from calculation. If 50% (5) or fewer of the 11 questions used in the calculation of Emotional Well-Being score have missing item score, then the scale score is calculated by multiplying the mean of the non missing item scores by 25. If 6 or more of the 11 item scores are missing then the scale score is not calculated and should be set at missing. Multiplying by 25 transforms

Confidential

the scale score to a 0 to 100 scale, with 0 reflecting the worst level of emotional well-being measurable by the scale and 100 reflecting the best.

1.c Work

| Work | Used in calculation of domain score? |
|--|--|
| 22. Are you currently working? | - |
| 23. Feeling distracted | Yes |
| 24. Feeling like I couldn't concentrate | Yes |
| 25. Having to take a break from work | Yes |
| 26. Having to change the way I work (such as the way I read, look at a computer, or work outside) | Yes |
| 27. Having to change my work environment (such as how close I am to an air conditioning or heating vent) | Yes |

| Response for question 22 | Original response code | Item score |
|--------------------------|---------------------------|------------|
| Yes | 1 | 1 |
| No | 2 | 0 |

| Response for questions 23 to 27 | Original response code | Item score If Response for question 22=0 | Item score If Response for question 22=1 |
|---------------------------------|------------------------------|--|--|
| None of the time | 1 | Missing | 4 |
| A little of the time | 2 | Missing | 3 |
| Some of the time | 3 | Missing | 2 |
| Most of the time | 4 | Missing | 1 |
| All of the time | 5 | Missing | 0 |

5 questions are included in the Work Limitations domain. If 50% (2) or fewer of the 5 questions used in the calculation of the Work Limitations score have missing item scores, then the scale score is calculated by multiplying the mean of the non missing item scores by 25. If 3 or more of the 5 item scores are missing then the scale score is not calculated and should be set to missing. Multiplying by 25 transforms the scale score to a 0 to 100 scale, with 0 reflecting the greatest degree of limitation at work measurable by the scale and 100 reflecting the least limitation at work.

Module 2:

Confidential Final Version 1.0, 2021-05-20 Dry eye Treatment satisfaction & Bother module (10 questions) comprising 2 QoL domains: 2.a "Treatment satisfaction / Happiness" and 2.b "Treatment-related bother".

2.a Treatment - In general

| Treatment in General | Used in calculation of domain score? |
|--|--|
| 1. OVER THE LAST TWO WEEKS, how often did you use | - |
| treatment for your dry eyes? | |
| 2. I was happy with how quickly my treatments worked | Yes |
| 3. I was happy with how long the effects of my | Yes |
| treatments lasted | |
| 4. The treatments I used completely eliminated my dry | Yes |
| eye symptoms | |
| 5. The treatments I used relieved most of my dry eye | Yes |
| symptoms | |
| 6. I was bothered by how often I had to use dry eye | Yes |
| treatments | |

| Response for question 1 | Original response code | Item score |
|-------------------------|------------------------------|------------|
| None of the time | 1 | 0 |
| A little of the time | 2 | 1 |
| Some of the time | 3 | 2 |
| Most of the time | 4 | 3 |
| All of the time | 5 | 4 |

| Response for questions 2 to 5 | Original response code | Item score If Response for question 1 = 0 | Item score If Response for question 1 > 0 or missing |
|----------------------------------|------------------------------|---|---|
| None of the time | 1 | Missing | 0 |
| A little of the time | 2 | Missing | 1 |
| Some of the time | 3 | Missing | 2 |
| Most of the time | 4 | Missing | 3 |
| All of the time | 5 | Missing | 4 |
| Response for question 6 | | | |
| None of the time | 1 | Missing | 4 |
| A little of the time | 2 | Missing | 3 |
| Some of the time | 3 | Missing | 2 |
| Most of the time | 4 | Missing | 1 |

Confidential

Final Version 1.0, 2021-05-20

Statistical Analysis Plan

| All of the time | 5 | Missing | 0 |
|-----------------|---|---------|---|

5 questions are included in the Treatment Satisfaction/Happiness scale score. If 50% (2) or fewer of the 5 questions used in the calculation of Treatment Satisfaction/Happiness score have missing item score, then the scale score is calculated by multiplying the mean of the non missing item score by 25. If 3 or more of the 5 item scores are missing then the scale score is not calculated and should be missing. Multiplying by 25 transform the scale score to a 0 to 100 scale, with 0 reflecting the lowest level of satisfaction/happiness with treatment measurable by the scale and 100 reflecting the highest level of satisfaction/happiness with treatment.

2.b Treatment- Eye Drops

| Treatment- Eye Drops | Used in calculation of domain score? |
|--|--|
| 7. Do you ever use eye drops to treat your dry eyes? | - |
| 8. I was bothered by blurriness shortly after using my eye | Yes |
| drops | |
| 9. I was embarrassed when I had to use my eye drops | Yes |
| 10. I felt like I could not go anywhere without my eye drops | Yes |

| Response for question 7 | Original response code | Item score |
|-------------------------|---------------------------|------------|
| Yes | 1 | 1 |
| No | 2 | 0 |

| Response for question 8 to 10 | Original response code | Item score If Response for question 1 = 0 | Item score If Response for question 1 > 0 |
|----------------------------------|------------------------------|---|---|
| None of the time | 1 | Missing | 4 |
| A little of the time | 2 | Missing | 3 |
| Some of the time | 3 | Missing | 2 |
| Most of the time | 4 | Missing | 1 |
| All of the time | 5 | Missing | 0 |

3 questions are included in the Treatment-Related Bother scale score. If 50% (1) or fewer of the 3 questions used in the calculation of Treatment-Related Bother scale score have missing item scores, then the scale score is calculated by multiplying the mean of the non missing item score by 25. If 2 or more of the 3 item scores are missing then the scale score is not calculated and should be set at missing. Multiplying by 25 transforms the scale score to a 0 to 100 scale, with 0 reflecting the greatest degree of treatment related bother measurable by the scale and 100 reflecting the lowest degree of treatment-related bother.

Confidential

Final Version 1.0, 2021-05-20

Module 3:

Dry eye Symptom bother (20 questions) comprising a unique domain.

| Symptom Bother | Used in calculation of domain score? |
|---|--|
| 1.OVER THE LAST TWO WEEKS, how often did you | Yes |
| experience dry eye symptoms? | |
| 2. Eyes that felt gritty or sandy | Yes |
| 3. Felt like I needed to close my eyes even though I was not | Yes |
| tired | |
| 4. Burning or stinging eyes | Yes |
| 5. Tired eyes | Yes |
| 6. Blurry vision | Yes |
| 7. Itchy eyes | Yes |
| 8. Irritated eyes | Yes |
| 9. Eyes that felt like they had been scratched by something | Yes |
| 10. Eye dryness | Yes |
| 11. Mucus in, around, or coming out of my eyes | Yes |
| 12. Puffy or swollen eyes | Yes |
| 13. Eye redness | Yes |
| 14. Aching or sore eyes | Yes |
| 15. Felt like something was in my eye | Yes |
| 16. Frequent and/or rapid blinking | Yes |
| 17. Difficulty blinking because of little or no moisture in my eyes | Yes |
| 18. Sensitivity to light, glare, and/or wind | Yes |
| 19. Sensitivity to recirculated air (such as air conditioning and | Yes |
| heat) | |
| 20. Headaches associated with dry eye symptoms | Yes |

| Response for question 1 | Original response code | Item score |
|-------------------------|---------------------------|------------|
| None of the time | 1 | 0 |
| A little of the time | 2 | 1 |
| Some of the time | 3 | 2 |
| Most of the time | 4 | 3 |
| All of the time | 5 | 4 |

| Response for questions 2 to 20 | Original response code | Item score |
|--|---------------------------|------------|
| I did not have this symptom / Not applicable | 6 | 0 |
| Not at all | 7 | 1 |

Confidential

Statistical Analysis Plan

Protocol: NGF0120

| Slightly | 8 | 2 |
|------------|----|---|
| Moderately | 9 | 3 |
| Very much | 10 | 4 |

All questions are included in the Symptom Bother scale score. If 50% (10) or fewer of the 20 questions used in the calculation of Symptom Bother scale score have missing item scores, then the scale score is calculated by multiplying the mean of the non missing item score by 25. If 11 or more of the 20 item scores are missing then the scale score is not calculated and should be set at missing. Multiplying by 25 transforms the scale score to a 0 to 100 scale, with 0 reflecting the greatest degree of treatment related bother measurable by the scale and 100 reflecting the lowest degree of treatment-related bother.

Change from baseline of above-defined subscores will be summarized as a continuous variable at each visit, and mean changes from baseline of all the subscores will be graphically presented (e.g. radar plot) for each visit.

• EQ-5D-5L change from baseline at week 4, 8, and week 32

Change from baseline of each dimension score and overall score of health today will be summarized as a continuous variable at each visit, and mean changes from baseline of all the dimension scores will be graphically presented (e.g. radar plot) for each visit.

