3. OVERALL STUDY DESIGN AND INVESTIGATIONAL PLAN

3.1. STUDY OBJECTIVES

Primary Objective

The primary objective of this study is to evaluate the safety and efficacy of OXERVATETM 0.002% (20 mcg/mL) cenegermin-bkbj ophthalmic solution administered 6 times daily for 8 weeks on the ocular surface, visual function and quality of life in patients with Stage 1 NK.

Secondary Objective

The secondary objective is to evaluate patients who heal at week eight and remain healed (as defined in section 3.3) throughout the follow-up period. In addition, the study aims to evaluate the percentage of subjects that achieve an improvement in corneal sensitivity as measured by the Cochet-Bonnet aesthesiometer at 4 and 8 weeks, and by the last visit week 32.

Exploratory Objectives

The exploratory objectives are to evaluate change from baseline to weeks 4 & 8 in Schirmer I and the Tear Film Break-Up Time (TFBUT) change from baseline to weeks 4 & 8.

Additional Objectives (site specific)

Analysis to evaluate the change from baseline at week 8 and week 24 in confocal microscopy and anterior segment OCT.

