Patients who meet the definition of Deterioration or No Improvement in the study eye at week 8 and during the follow up period, will be discontinued from the study and treated as appropriate at the discretion of the investigator.

Deterioration or No Improvement is defined by any of the following:

- In the Study Eye, the FCS is unchanged (Grade=3) from baseline in the qualifying NEI zone.
- At the PIs discretion, in the study eye there is a progression from baseline in the non-qualifying zones
- decrease in BCDVA by >10 ETDRS letters from baseline.
- progression in staining to a PED or corneal melting or perforation
- onset of infection
- Require an ocular surgical procedure, including the need for a corneal transplant.

Note: If there is a deterioration in the non-study eye, the Investigator may discontinue treatment in that eye and initiate alternative treatment at their discretion in the non-study eye, but continue following the study eye per protocol.

[figure not shown]
All patients will attend the following clinic visits in the following sequence:

- Screening (Visit 1/Day -14)
- Baseline and First Study Product Pick-Up (Visit 2/Day 0)
- Product Pick-Up (Visit 3/Week 2)
- Treatment Assessment and Study Product Pick-Up (Visit 4/Week 4)
- Product Pick-Up (Visit 5/Week 6)
- End of 8-week Treatment (Visit 6/Week 8)
- Follow-Up and Final Study Visit (Visit 7/Week 32).

The trial structure for subjects is shown in **Figure 1**

Figure 1 Study Schematic

Any subject who meets the definition of experiencing a deterioration in the study eye, will be discontinued from the study, and followed per the Investigator's discretion.

If there is a deterioration in the non-study eye, the Investigator may discontinue treatment in that eye and initiate alternative treatment at their discretion in the non-study eye, but continue following the study eye per protocol.

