6.2. EARLY WITHDRAWAL FROM STUDY

A premature discontinuation will occur when a patient who signed the ICF ceases participation in the study, regardless of circumstances, before the completion of the study protocol procedures. Patients can be prematurely discontinued from the study for one of the following reasons:

- Progression from Stage 1 to Stage 2 or Stage 3 NK, or corneal melting/perforation
- At the PI discretion patient is considered to be a non-responder (no improvement from baseline).
- In the qualifying/Study Eye, the FCS is unchanged (Grade=3) from baseline after 8 weeks of treatment in the qualifying NEI zone or there is an increase in FCS ≥1 within a non-qualifying NEI zone in the same eye.
- Decrease in BCDVA by >10 ETDRS letters
- Onset of infection (bacterial or viral)
- Protocol violation, including lack of compliance defined as <80% of doses taken based on diary documentation between treatment clinic visits.
- Withdrawal of consent
- Lost to follow-up during the treatment period (Every effort must be made to contact the patient; a registered letter must be sent)
- Study terminated by the Sponsor
- Other reasons, such as administrative reasons or pregnancy
- Development of AE or unacceptable toxicity per the investigator's discretion, precluding further therapy with the study drug.
- Severe protocol violations, such as an incorrect treatment administration, or a concomitant use of not permitted medications. Before removal, these cases should first be discussed with Dompé.

The reasons for premature discontinuation from the study will be reflected on the Study Termination Record of the CRF. For patients who prematurely discontinue, Visit 6 procedures will be completed, and these patients will be considered off study and will no longer be followed.

For patients that discontinue prematurely, the investigator should refer patients for further treatment as appropriate.

Replacement Procedures

Patients in this study who prematurely discontinue before completion of 8 weeks of treatment with OxervateTM will be replaced. Patients prematurely discontinuing during follow up treatment will not be replaced.

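### Week 32 sensitivity, vision, tear and quality-of-life results come from patients selected partly on response, because poor responders leave at Week 8 and SAP 5.2 uses observed cases only

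*SAP*

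**What the plan says.** **Who leaves.** Protocol 3.3 (and the synopsis) sets a removal rule for those that "meet the definition of Deterioration or No Improvement in the study eye at week 8 and during the follow up period, will be discontinued". The criteria include "In the Study Eye, the FCS is unchanged (Grade=3) from baseline in the qualifying NEI zone" and "decrease in BCDVA by >10 ETDRS letters from baseline", together with progression, infection and need for ocular surgery. Protocol 6.2 repeats the staining and vision criteria under a permissive lead-in: "Patients can be prematurely discontinued from the study for one of the following reasons".

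**What happens to them.** They have the Visit 6 assessments, and then "these patients will be considered off study and will no longer be followed". Protocol 3.3 says the same.

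**Who stays.** Completely healed patients, and non-healed patients at Grade 2 who meet no discontinuation criterion, go on to Week 32.

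**What is reported at Week 32.** The secondary objective in Protocol 3.1 covers improvement in "corneal sensitivity as measured by the Cochet-Bonnet aesthesiometer at 4 and 8 weeks, and by the last visit week 32". SAP 5.2 lists Week 32 results for corneal sensitivity (mean change and percentage improved), Schirmer, TFBUT, IDEEL, EQ-5D-5L and vision ("Mean change in BCDVA from baseline to Week 4, 8, and week 32"). SAP Appendix 2 assigns all these tables to the Full Analysis Set. SAP 5.2 says the secondary analyses "will be performed based on the observed cases in the FAS population. No missing data imputation will be considered".

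**What covers the gap.** The carry-forward analyses in SAP 5.1 apply only to Week 8 epithelial healing. SAP 2.11 makes observed cases the default. Protocol 9.3.4 leaves imputation details to the SAP, which gives none for Week 32. Only the sustained-healing endpoints have a second denominator, the Full Treated Set (FTS).

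**The concern.** The missing Week 32 data are created by the design, and they depend on outcome. A patient whose study eye is still Grade 3 at Week 8, or who has lost more than 10 letters, has a Week 8 value but, once discontinued, no Week 32 value. In one table the Week 8 and Week 32 columns then describe different patients, and a rise or a plateau between them can come from the change of patients rather than from a lasting effect.

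The secondary objective asks what share of subjects have improved sensitivity by Week 32. The planned table answers that for the patients retained. The study has no control arm and no hypothesis test, so these descriptive estimates are the result, and readers will take the Week 32 columns as evidence of durability.

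**Working it through.** **1. The plan's own figure.** Protocol 9.1 gives lower 95% limits of 40% and 54% for healing of 58% and 72% with n = 35. The Clopper-Pearson lower limit, the 2.5% quantile of Beta(x, n − x + 1) with x = 35 × 0.58 and 35 × 0.72, is 40.2% and 54.3%. The figures reproduce. They concern Weeks 4 and 8 only and do not depend on this point.

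**2. How many could leave.** The documents give no expected number. At 72% healing about 0.28 × 35 ≈ 10 patients are unhealed at Week 8. Those still at Grade 3 are a subset, so staining alone could remove anywhere from 0 to about 10. Vision loss and the other criteria could add to this.

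**3. BCDVA.** Assumptions, none from the documents:
- Week 8 change in letters is normal with mean m = 0 or 5 and SD = 7, 10 or 13.
- Everyone losing more than 10 letters leaves, and nobody leaves for another reason.
- The Week 8 to Week 32 correlation is 0.7, with equal SDs at the two visits.

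With z = (10 + m)/SD:
- share removed = Φ(−z)
- rise in the retained Week 8 mean = SD × φ(z)/Φ(z)
- shift carried to Week 32 = 0.7 × that rise

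| m | SD | z | Removed | Rise at Week 8 | Shift at Week 32 |
|---|---|---|---|---|---|
| 0 | 7 | 1.43 | 8% | 1.1 | 0.8 |
| 0 | 10 | 1.00 | 16% | 2.9 | 2.0 |
| 0 | 13 | 0.77 | 22% | 5.0 | 3.5 |
| 5 | 7 | 2.14 | 2% | 0.3 | 0.2 |
| 5 | 10 | 1.50 | 7% | 1.4 | 1.0 |
| 5 | 13 | 1.15 | 12% | 3.0 | 2.1 |

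Worked row (m = 0, SD = 10): 10 × 0.2420/0.8413 = 2.88, and 0.7 × 2.88 = 2.0 letters. SAP 5.2 equates 15 letters with 0.3 logMAR, or 0.02 per letter. The range of 0.2 to 3.5 letters is therefore 0.004 to 0.07 logMAR towards improvement, which appears as a lower logMAR mean.

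**4. Corneal sensitivity, responder rate.** Assume 35 treated patients, 7 removed, and 17 of the 28 retained improved.
- Observed cases: 17/28 = 61% (exact 95% CI 41 to 78).
- All removed counted as not improved: 17/35 = 49% (31 to 66).
- All removed counted as improved: 24/35 = 69% (51 to 83).

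The first figure always lies between the other two.

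**5. Corneal sensitivity, size of bias.** If a fraction p_r of retained and p_d of removed patients have improved, and d of 35 are removed, the observed rate exceeds the all-patient rate by (d/35) × (p_r − p_d).

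| p_r, p_d | d = 2 | d = 4 | d = 7 | d = 10 |
|---|---|---|---|---|
| 60%, 60% | 0 | 0 | 0 | 0 |
| 60%, 30% | 1.7 points | 3.4 | 6.0 | 8.6 |
| 70%, 20% | 2.9 points | 5.7 | 10.0 | 14.3 |

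**6. Whether another rule closes the gap.**
- Tabulating on the FTS (SAP 5.4) does not. A patient removed at Week 8 after full treatment is in the FTS but has no Week 32 value.
- Assigning data to the nearest scheduled visit (SAP 2.5) does not help for a Week 8 exit. The midpoint between Day 56 and Day 224 is Day 140, so only a late follow-up exit might count as Week 32.

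**The case against.** The case on the other side has substance, and much of it limits the point.

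- **Certainty of removal.** A reader might infer that every patient more than 10 letters worse is taken out. Protocol 3.3 supports this, but 6.2 lists the same criterion as a permitted reason. Discontinuation is outcome-related under either wording. If it is applied only in part, the BCDVA shift is smaller than tabulated.
- **Direction.** A reader might infer that all Week 32 results are biased towards benefit. The documents support that only for BCDVA. Sensitivity, Schirmer, TFBUT, IDEEL and EQ-5D-5L are not named removal criteria, and with equal rates in retained and removed patients the bias is zero.
- **Healed patients only.** A reader might infer this about Week 32. It is wrong, because Grade 2 non-healers who meet no criterion stay in.
- **Scope.** Protocol 7.1.1 lists mean BCDVA change to Week 8 only, and Schirmer and TFBUT to Weeks 4 and 8. Week 32 for these is a SAP addition. Of the affected endpoints, those listed at Week 32 in the protocol are sensitivity and quality of life, where direction is least certain.
- **Visibility.** The SAP reports the number of observations per visit, visit completion and reasons for discontinuation, and Protocol 9.3.4 asks for the percentage missing. SAP 5.2 says openly that it uses observed cases. SAP 2.10 calls all efficacy analyses exploratory.
- **Remedy.** Counting discontinued patients as not improved lets staining or vision failure decide a sensitivity outcome, which is a choice of estimand. Carrying an exit value across 24 weeks assumes no later change and understates uncertainty.

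The first four limits stand and are built into the conclusion. Visibility stands as mitigation: a falling n shows that patients have gone, but not how they differed. The remedy objection stands against making either analysis the main one, but not against showing them as bounds.

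**Conclusion.** The point holds in a bounded form. Week 32 results on observed cases describe patients selected partly on response, and SAP 5.2 has no analysis that accounts for this outside the healing endpoints.

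For BCDVA the upward bias in letters is near-certain in direction, given a positive Week 8 to Week 32 correlation. It is about 0.2 to 3.5 letters over the assumed means, SDs and correlation. For sensitivity, tear measures and quality of life, upward bias is plausible, but neither its presence nor its size can be derived from the documents.

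The 12-point gap between 61% and 49% might be read as the bias. It is not: 49% is a worst-case bound under one assumed number of removals, and the true all-patient value in that example could lie anywhere from 49% to 69%.

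Because the study is exploratory and without formal tests, this is a change the plan should make rather than a fault that invalidates it.

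**What to change.** In SAP 5.2 and the matching Appendix 2 shells:

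1. Label the observed-case Week 32 tables 'patients retained after Week 8', and show the Week 8 change in those same patients beside their Week 32 change.
2. Add a sensitivity analysis of the Week 32 corneal-sensitivity responder rate with all FAS patients in the denominator and discontinued patients counted as not improved. Present it as a conservative bound, not as the main estimate. The SAP already gives sustained healing a second, wider denominator. State how a late exit visit that SAP 2.5 would assign to Week 32 is handled.
3. Optionally, for continuous endpoints, add a summary using the exit (Visit 6 assessment) value for discontinued patients, as supportive only.

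Separately, Protocol 3.3 and 6.2 must be reconciled on whether meeting the criteria requires or permits discontinuation, so that the retained group is defined.

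The cost is SAP wording and a few extra table columns. No new data are needed, because exit assessments are already planned. The Week 32 figures may look less favourable. The change does not address the discretionary topical treatment that retained Grade 2 patients may receive, which also affects Week 32.
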